6.1.4 Treatment duration

The planned duration of treatment is 52 weeks. Subjects may be discontinued from treatment earlier due to unacceptable toxicity or at the discretion of the investigator or the subject. After completion of Treatment Period 2, subjects may continue treatment in a planned extension study or enter the 8-week post-treatment Follow-up in this study.

6.2 Other treatment(s)

6.2.1 Concomitant therapy

The investigator must instruct the subject to notify the study site about any new medications taken after enrolling in the study. All medications, procedures and significant non-drug therapies (including physical therapy and blood transfusions) administered after the subject was enrolled into the study must be recorded on the appropriate electronic case report/record form (eCRF).

Each concomitant drug must be individually assessed against all exclusion criteria/prohibited medication. If in doubt, the investigator should contact the Novartis medical monitor before randomizing a subject or allowing a new medication to be started.

6.2.1.1 Permitted concomitant therapy

Antiseptic Therapy

Subjects should be instructed to use daily topical over-the-counter antiseptics on the skin areas affected by HS lesions following the local standard practice.

Wound Care

Concomitant use of wound care dressings on HS wounds is allowed following the local standard practice.

6.2.1.2 Permitted concomitant therapy requiring caution and/or action

Antibiotics

Systemic antibiotics for the treatment of acute systemic infectious disease both related or unrelated to HS (e.g. pneumonia, cellulitis) are allowed as medically warranted during the study.

Systemic antibiotics for the treatment of HS are only allowed as rescue medication as described in [Section 6.2.3](#) below.

For subjects entering the study in the antibiotic strata, treatment with the following tetracyclines on a stable dose is allowed in Treatment Period 1:

- Tetracycline up to 500 mg twice a day
- Minocycline up to 100 mg twice a day
- Doxycycline up to 100 mg twice a day

Analgesics

Subjects will be required to wash out opioid analgesics (including tramadol) for 14 days prior to Baseline. This includes opioids for both HS-related pain and non-HS-related pain.

Subjects on a stable dose of a non-opioid analgesic ("as needed" is not considered stable) may continue the analgesic, provided the dose is stable for 14 days prior to Baseline and is anticipated to remain stable for at least 16 weeks of treatment.

In case a subject presents with uncontrolled pain related to HS during the study, ibuprofen and acetaminophen (paracetamol) are permitted.

If HS-related pain is uncontrolled with ibuprofen or acetaminophen (paracetamol) at the maximal dose as per local label during the trial, subjects can be prescribed tramadol (at a dose of up to 100 mg orally every 4 hours), not to exceed 400 mg/24 hours.

Information on the concomitant use of analgesics should be recorded by the subject in the eDiary and reviewed by the investigator at the scheduled visits.

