6.2.2 Prohibited medication

Use of the treatments displayed in [Table 6-2](#) that could confound the efficacy assessment or could put the patient at an additional safety risk are not allowed during the study and wash-out

periods for these treatments prior to randomization are indicated in the table. If the use of these treatments is required, then the subject should not be randomized.

The investigator should instruct the subject to notify the study site about any new treatments he/she takes after the start of study treatment. All prohibited medications and significant non-drug therapies administered after the subject starts study treatment must be recorded in the eCRF.

If a prohibited treatment listed in [Table 6-2](#) is used during the study, the subject should discontinue use of the prohibited treatment if he/she wishes to continue in the study. At the discretion of the investigator, if the subject's use during the study of a prohibited treatment presents undue safety risk for the subject, the subject should be discontinued from study treatment.

Table 6-2 Prohibited medication

Medication	Prior to randomization	Use between randomization and last dose of study drug	Action taken
Prior treatment with secukinumab or other agents blocking IL-17 A/F or IL-17R	Not allowed	Not allowed	Subject not eligible
Systemic biological immunomodulating treatment (e.g. adalimumab, infliximab, ustekinumab, anakinra, natalizumab)	12 weeks wash-out period or 5 half-lives, whichever is longer	Not allowed	Discontinue use or discontinue study treatment
Systemic non-biologic immunomodulating treatment (e.g. methotrexate (MTX), cyclosporine A, retinoids, apremilast)	28 days wash-out period required	Not allowed	Discontinue use or discontinue study treatment
Topical antibiotic therapies for the treatment of HS	14 days wash-out period required	Not allowed until Week 16	Discontinue use or discontinue study treatment if not medically warranted
Antibiotics for the treatment of HS (non-antibiotic strata)	28 days wash-out period required	Not allowed until Week 16, except for rescue treatment	Discontinue use or discontinue study treatment if not medically warranted
Systemic corticosteroids for the treatment of HS	28 days wash-out period required	Not allowed	Discontinue use or discontinue study treatment
Opioid analgesics	14 days wash-out period required	Not allowed	Discontinue use or discontinue study treatment

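### Section 6.2.1.2 permits tramadol, which it classes as an opioid, for uncontrolled HS pain, but the opioid row of Table 6-2 bars opioids from randomization to last dose with no exception

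*Protocol*

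**What the plan says.** Protocol Section 6.2.1.2 deals with tramadol twice. The wash-out rule puts it in the opioid class: "Subjects will be required to wash out opioid analgesics (including tramadol) for 14 days prior to Baseline". The on-study rule then allows it as a last step. If HS pain is not controlled by ibuprofen or paracetamol at the highest labelled dose, "subjects can be prescribed tramadol (at a dose of up to 100 mg orally every 4 hours), not to exceed 400 mg/24 hours".

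Section 6.2.2 introduces Table 6-2 by saying that treatments "that could confound the efficacy assessment or could put the patient at an additional safety risk are not allowed during the study". One row is headed "Opioid analgesics". It asks for a 14-day wash-out, gives 'Not allowed' for the time from randomization to the last dose of study drug, and names as the action stopping either the opioid or study treatment. The row has no exception and does not refer to Section 6.2.1.2. For anyone who uses a listed treatment, Section 6.2.2 says "the subject should discontinue use of the prohibited treatment if he/she wishes to continue in the study". Section 9.1.1 lists continuing use of a prohibited treatment among the reasons for which study treatment must be stopped.

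SAP Section 2.5.2 plans a summary of HS pain medication and names tramadol beside ibuprofen and paracetamol.

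**The concern.** Two operative rules give opposite instructions for the same drug over the same period. Sites are sent to the prohibiting rule, because Section 6.2.1 states: "Each concomitant drug must be individually assessed against all exclusion criteria/prohibited medication". A site that checks tramadol against Table 6-2 finds a ban.

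That site could do one of three things, all contrary to the apparent intent:

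- Withdraw analgesia from a patient whose pain is uncontrolled on first-line drugs at full dose.
- Allow the drug and record a protocol deviation.
- Stop study drug if tramadol use continues, because Section 9.1.1 makes that mandatory.

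The third has a possible analysis consequence. Under Protocol Section 12.4.3, if treatment stops for a reason other than an adverse event or lack of efficacy, data collected afterwards are set aside. The missing values are then imputed under a missing-at-random assumption. Whether a stop of this kind would be given such a reason is not stated.

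The patients concerned are those with uncontrolled HS pain, and pain response (NRS30) is formally tested as H7 and H8.

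**Working it through.** No figure in the plan depends on this point, so the check is a comparison of text.

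| Question | Section 6.2.1.2 | Table 6-2, opioid row |
|---|---|---|
| Is tramadol covered? | Yes, named as an opioid | Yes, by class |
| Before baseline or randomization | 14-day wash-out | 14-day wash-out |
| On study treatment | Permitted after maximal ibuprofen or paracetamol, up to 400 mg in 24 hours | Not allowed |
| Exception or cross-reference | None to Table 6-2 | None to Section 6.2.1.2 |
| Action if used | None required | Stop the opioid or stop study drug |

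**Step 1: same drug.** Because the wash-out sentence names tramadol as an opioid, the row cannot be read as leaving it out.

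**Step 2: same period.** The permission applies during the trial. The table column runs from randomization to the last dose of study drug. They overlap throughout both treatment periods, including Week 16. After the last dose the cell no longer applies.

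**Step 3: is there a reconciling rule?** Section 6.2.3 (rescue medication) covers antibiotics and lesion intervention only. Sections 6.2.2 and 9.1.1 contain no analgesic exception. SAP Section 2.5.2 shows that tramadol use is expected but states no order of precedence.

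**Step 4: how do nearby rows handle overlaps?** Section 6.2.1.2 says "For subjects entering the study in the antibiotic strata, treatment with the following tetracyclines on a stable dose is allowed in Treatment Period 1", and the HS antibiotic row is accordingly limited to the non-antibiotic strata. The same row exempts rescue treatment. The HS surgery row exempts procedures allowed as rescue. Beside rows that state their exceptions, a bare 'Not allowed' reads as having none.

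**Step 5: is the dose wording itself consistent?** Dosing 100 mg every 4 hours gives 24/4 = 6 doses, or 6 × 100 = 600 mg in 24 hours, which exceeds 400 mg. The 400 mg cap is in the same sentence and governs, so this is not a second error.

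**The case against.** The strongest reply is that a specific rule overrides a general one. Section 6.2.1.2 sits under a heading for permitted therapy that needs caution, and it gives the drug, the trigger and the dose cap. A careful reader would take it as an exception to a class-level row, and SAP Section 2.5.2 supports that reading. A site in doubt is told to contact the medical monitor "before randomizing a subject or allowing a new medication to be started". On this view all that is missing is a cross-reference.

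This stands as evidence of intent, and it limits the consequence. It does not remove the contradiction. No passage states that precedence, Section 6.2.1 sends sites to the table, and Section 9.1.1 attaches a mandatory stop to what the table prohibits. The permission is also optional, so a site that never prescribes tramadol breaches neither rule.

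A reader might infer more than the documents support in four places:

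- **That any tramadol use on study conflicts with the row.** The table column ends at the last dose, so use in post-treatment follow-up is outside the cell, although the introductory sentence of Section 6.2.2 is broader.
- **That tramadol is the only permission not carried into the table.** Section 6.2.1.2 also allows systemic antibiotics for acute systemic infection, including infection related to HS. The use column of the HS antibiotic row exempts rescue treatment only. Its action column allows for medically warranted use, which covers the case in part. A count of matched and unmatched permissions therefore depends on how this one is classed.
- **That a tramadol deviation would merely be tabulated.** SAP Section 2.4 tabulates deviations, and SAP Table 5-2 lists no exclusion identified as prohibited medication. But this SAP covers the final Week 52 analysis. Its Sections 1 and 1.2.1 place the tested endpoints and their estimands in a separate Week 16 SAP that is not available here.
- **That NRS30 is compromised.** No tramadol rate, direction of effect or difference between arms is given.

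**Conclusion.** The opioid row of Table 6-2 is wrong as written. Tramadol given as Section 6.2.1.2 permits, between randomization and the last dose of study drug, contradicts it. The severity is minor.

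The size cannot be computed. The documents give no expected frequency of tramadol use or of treatment stops for this reason, and none of the stated powers uses such a figure. An effect on NRS30 through uneven site practice is possible but unquantified. Analgesic use is recorded in the eDiary, so it could be examined. For the Week 52 analysis sets, no prohibited-medication exclusion is listed. Handling in the Week 16 analysis is unknown.

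The choice of which rule to correct rests on one inference: that the permission is intended. Its detail and SAP Section 2.5.2 both support this. If the ban were intended instead, the tramadol sentence in Section 6.2.1.2 would have to go.

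**What to change.** In the opioid row of Table 6-2, change the on-study entry to: *Not allowed, except tramadol as permitted in Section 6.2.1.2*. Use within that permission then falls outside prohibited treatment for Sections 6.2.2 and 9.1.1, and neither section needs rewording.

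The cost is one phrase in one table cell. Hypotheses, alpha, sample size, models and data collection are unchanged.

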6.2.2 Prohibited medication

Use of the treatments displayed in [Table 6-2](#) that could confound the efficacy assessment or could put the patient at an additional safety risk are not allowed during the study and wash-out

periods for these treatments prior to randomization are indicated in the table. If the use of these treatments is required, then the subject should not be randomized.

The investigator should instruct the subject to notify the study site about any new treatments he/she takes after the start of study treatment. All prohibited medications and significant non-drug therapies administered after the subject starts study treatment must be recorded in the eCRF.

If a prohibited treatment listed in [Table 6-2](#) is used during the study, the subject should discontinue use of the prohibited treatment if he/she wishes to continue in the study. At the discretion of the investigator, if the subject's use during the study of a prohibited treatment presents undue safety risk for the subject, the subject should be discontinued from study treatment.

Table 6-2 Prohibited medication

Medication	Prior to randomization	Use between randomization and last dose of study drug	Action taken
Prior treatment with secukinumab or other agents blocking IL-17 A/F or IL-17R	Not allowed	Not allowed	Subject not eligible
Systemic biological immunomodulating treatment (e.g. adalimumab, infliximab, ustekinumab, anakinra, natalizumab)	12 weeks wash-out period or 5 half-lives, whichever is longer	Not allowed	Discontinue use or discontinue study treatment
Systemic non-biologic immunomodulating treatment (e.g. methotrexate (MTX), cyclosporine A, retinoids, apremilast)	28 days wash-out period required	Not allowed	Discontinue use or discontinue study treatment
Topical antibiotic therapies for the treatment of HS	14 days wash-out period required	Not allowed until Week 16	Discontinue use or discontinue study treatment if not medically warranted
Antibiotics for the treatment of HS (non-antibiotic strata)	28 days wash-out period required	Not allowed until Week 16, except for rescue treatment	Discontinue use or discontinue study treatment if not medically warranted
Systemic corticosteroids for the treatment of HS	28 days wash-out period required	Not allowed	Discontinue use or discontinue study treatment
Opioid analgesics	14 days wash-out period required	Not allowed	Discontinue use or discontinue study treatment
Surgeries for the treatment of HS other than allowed as rescue therapy	Not allowed within 6 weeks prior to randomization	Not allowed until Week 16	Discontinue study treatment

Medication	Prior to randomization	Use between randomization and last dose of study drug	Action taken
Live vaccines	Not allowed within 6 weeks prior to randomization	Not allowed	Discontinue study treatment
Any investigational treatment or participation in any interventional trial	28 days or 5 half-lives (whichever is longer) wash-out period required	Not allowed	Discontinue study treatment

6.2.3 Rescue medication

Antibiotics

At Week 4, 8 and 12, if a subject experiences an increase in their AN count (for example, the total count is greater-than-or equal-to 150% of the weighted average of screening and baseline AN count ([Section 12.4.1](#))) with a minimum increase of 3 lesions, oral antibiotics rescue medication can be used. This applies only to Treatment Period 1.

Subjects who qualify for rescue medication may initiate antibiotic treatment with minocycline or doxycycline up to 100 mg bid. The dosing regimen must remain stable until Week 16. Except for current antibiotic use strata, concomitant use of antibiotic therapy for treatment of HS is otherwise not allowed. However, antibiotics are permitted to treat an acute infection if medically warranted ([Section 6.2.1.2](#)). Rescue antibiotic therapy should be captured in the source and on the appropriate eCRF.

Lesion Intervention

In the event of an acutely painful single lesion that requires an immediate intervention, the investigator will be allowed to perform an unplanned surgery/intervention for lesion such as excision, drainage or intra-lesion steroid administration at any time.

Other HS related surgery is not allowed until after Week 16.

All study visit evaluations must take place before any interventions are performed.

6.3 Subject numbering, treatment assignment, randomization

6.3.1 Subject numbering

Each subject is identified in the study by a Subject Number (Subject No.), that is assigned when the patient is enrolled for screening and is retained for the subject throughout his/her participation in the trial. A new Subject No. will be assigned if the subject is rescreened. The Subject No. consists of the Center Number (Center No.) (as assigned by Novartis to the investigative site) with a sequential subject number suffixed to it, so that each subject participation is numbered uniquely across the entire database. Upon signing the informed consent form, the patient is assigned to the next sequential Subject No. available within the electronic data capture (EDC) system.

The investigator or his/her staff will contact the IRT and provide the requested identifying information for the subject to register them into the IRT.

If the subject fails to be treated for any reason, the IRT must be notified within 2 days that the subject was not treated. The reason for not being treated will be entered on the appropriate eCRF.

6.3.2 Treatment assignment, randomization

The investigator or his/her delegate will contact the IRT after confirming that the subject fulfills all the inclusion/exclusion criteria. The IRT will assign a randomization number to the subject, which will be used to link the subject to a treatment arm and will specify a unique medication number for the package of study drug to be dispensed to the subject. The randomization number will not be communicated to the investigator or his/her delegate.

The randomization numbers will be generated using the following procedure to ensure that treatment assignment is unbiased and concealed from subjects and investigator staff. A patient randomization list will be produced by the IRT provider using a validated system that automates the random assignment of patient numbers to randomization numbers. These randomization numbers are linked to the different treatment arms, which in turn are linked to medication numbers. A separate medication list will be produced by or under the responsibility of Novartis Clinical Drug Supply using a validated system that automates the random assignment of medication numbers to packs containing the investigational drug(s).

Randomization will be stratified by region, concomitant antibiotic use (Yes/No) and body weight (weight < 90kg / ≥ 90kg).

The randomization scheme for subjects will be reviewed and approved by a member of the Randomization Group.

6.4 Treatment blinding

This is a double blind study. Subjects, investigator staff, persons performing the assessments, and Novartis Clinical Trial Team (CTT) will remain blind to the identity of the treatment from the time of randomization until database lock, using the following methods:

1. Randomization data are kept strictly confidential until the time of unblinding, and will not be accessible by anyone else involved in the study with the following exceptions:
 - Specific vendors whose role in trial conduct requires their unblinding (e.g., IRT)
 - Drug Supply Management
 - The designated Novartis study team members involved in the primary endpoint analysis
2. The identity of the treatments will be concealed by the use of study treatment that are all identical in packaging, labeling, schedule of administration, appearance and schedule of administration.

The randomization codes associated with subjects from whom PK samples are taken will be disclosed to the bioanalyst and pharmacokineticist (if required at primary endpoint analysis) who will keep serum concentrations confidential until database lock.

For subjects, investigators/site personnel and Novartis personnel working directly with the sites, unblinding will occur in the case of subject emergencies (see [Section 6.6.3](#)), and at the conclusion of the study. The appropriate personnel from the study site and Novartis will assess

whether the study treatment should be discontinued for any subject whose treatment code has been broken inadvertently for any reason.

At the time of a primary endpoint analysis after all subjects have completed Week 16, the designated Novartis personnel (e.g. biostatisticians and programmers involved in the analysis, key Global Team members) may have access to the unblinded results. Field monitors/clinical research associates will remain blinded until after final database lock. Subjects and site personnel directly involved in the conduct of the trial, i.e. investigator staff and persons performing the assessments, will remain blinded to individual treatment allocation until the conclusion of the study to ensure study integrity is maintained.

6.5 Dose escalation and dose modification

Investigational or other study treatment dose adjustments and/or interruptions are not permitted.

6.5.1 Dose modifications

Study treatment interruption is only permitted if, in the opinion of the investigator, a subject is deemed to be placed at a significant safety risk unless dosing is temporarily interrupted. In such cases, study treatment should be interrupted only during the time that this risk is present and ongoing. Study treatment can be restarted at the next scheduled visit after resolution of the safety risk.

These changes must be recorded on the appropriate eCRF.

6.5.2 Follow-up for toxicities

Not applicable.

6.6 Additional treatment guidance

6.6.1 Treatment compliance

All doses of study treatment administration will be recorded on the appropriate Dosage Administration Record eCRF page (visit specific and summary pages). For study treatment administration at home, the investigator must promote compliance by instructing the subject to administer the study treatment exactly as instructed and by stating that compliance is necessary for the subject's safety and the validity of the study. The subject must also be instructed to contact the investigator if he/she is unable for any reason to administer the study treatment. Compliance will be assessed by the investigator and/or study personnel at each visit using empty medication packaging, pre-filled syringe (PFS) and information provided by the subject. This information should be captured in the source document at each visit. All study treatment dispensed and returned must be recorded in the Drug Accountability Log. Compliance will also be assessed and confirmed by a field monitor by drug accountability logs, by documentation and information provided by IRT and by the qualified site personnel that is responsible for treatment dispensation, administration and accountability. Cross-checks should be performed for home administrations (H) and empty medication outer packing and patient's returned PFS should be collected for compliance checks by field monitors.

Pharmacokinetic parameters (measures of treatment exposure) will be determined in all subjects treated with secukinumab, as detailed in the Pharmacokinetics [Section 8.5.2](#).

